1.3.3 Rationale for dose selection

Olaparib will be administered at a dose of 300mg by mouth twice daily in tablet formulation. This dose is similar in terms of safety and efficacy to the FDA-approved dose of 400mg by mouth twice daily in capsule formulation. This dose was established in the phase I studies and was also employed in prior studies involving prostate cancer.

1.3.4 Rationale for correlative studies

1.3.4.1 Genetic mutation analysis in tumor

Tumors will be analyzed using the FoundationOne platform by Foundation Medicine (Cambridge, MA). This test sequences provides mutation analysis in 315 selected genes and rearrangement analysis in 28 genes. The genes include those commonly mutated (BRCA2, ATM, BRCA1, CHEK2, CDK12, RAD51, PALB2, FANCL). The analysis provides a depth of coverage of 500X, and is reported by variant analysis with regard to likely pathogenicity. By cataloging the mutations present in the primary tumors for subjects in the study, correlative analysis associating response with specific mutations can be performed. The testing will be inclusive of a sub-panel of genes of particular interest (ATM, BARD1, BRCA1, BRCA2, BRIP1, CDK12, CHEK1, FANCL, PALB2, PPP2R2A, RAD51B, RAD51C, RAD51D, and other DNA repair genes).

1.3.4.2 RNA expression array analysis in tumor

An alternative possibility for tumor sensitivity to olaparib is through epigenetic gene expression changes that may not be identified through genetic mutation analysis alone. In conjunction with the DNA mutation testing planned to be performed through Foundation Medicine, subjects will have tissue tested for RNA expression arrays for associating response to olaparib. For this assay, samples will be tested by GenomeDx (San Diego, CA) using the Decipher GRID microarray platform. The gene expression profile will be inclusive of a metastasis signature and olaparib-sensitivity signature. The metastatic signature has been validated in a cohort of patients with high risks for recurrence after primary prostate cancer therapy [24, 25], as well as in a cohort of patients undergoing salvage radiation therapy after biochemical recurrence of prostate cancer [26]. A post-hoc analysis will be performed to evaluate these signatures, and further determine a gene expression profile that predicts response to olaparib.

1.3.4.3 PARP-1 and γH2AX protein levels in tumor

Beyond the underlying genetic mutations in DNA repair genes and the associated RNA expression profiles, we are exploring whether baseline assessment of the PARP-1 enzyme or γH2AX protein positivity by immunohistochemistry is predictive of response. γH2AX is a protein that serves as a marker for double strand DNA breaks. PARP-1 is the primary molecular target for olaparib.

2. OBJECTIVES

2.1 Primary Objective

The primary objective is to estimate the response rate (PSA₅₀) to olaparib for patients with high-risk biochemically-recurrent prostate cancer. By estimating the PSA₅₀ response rate, this will serve as an initial exploration of olaparib's activity in this disease state.

2.2 Secondary Objectives

- To determine the safety/tolerability of olaparib in the biochemically-recurrent prostate cancer patient population.
- To estimate the median PSA progression-free survival.
- To estimate the median time to PSA doubling from baseline.
- To estimate the rate of durable undetectable PSA in patients responding to olaparib.

2.3 Correlative/Exploratory/Tertiary Objectives

- *(if an enriched population is not accrued)* To estimate PSA₅₀ response in “biomarker positive” patients, based upon FoundationOne tissue-based mutations in the pre-specified gene list (ATM, BARD1, BRCA1, BRCA2, BRIP1, CDK12, CHEK1, CHEK2, FANCL, PALB2, PPP2R2A, RAD51B, RAD51C, RAD51D, or other DNA repair genes).
- *(if an enriched population is not accrued)* To estimate PSA₅₀ response in “biomarker negative” patients, based upon tissue-based mutations in the pre-specified gene list.
- To estimate PSA₅₀ response rate for patients with and without a mutation on the pre-specified list, based upon plasma cell-free DNA analysis using the pre-specified gene list.
- To develop a genetic mutation signature associated with response to olaparib. For this objective, the biomarker signature will not be defined *a priori* but instead this will involve an exploratory analysis.
- To develop an RNA expression signature associated with response to olaparib.
- To investigate any association between PARP-1 and γH2AX protein levels in tumor with response to olaparib.
- To estimate median metastasis-free survival.
- To estimate median time to next anti-cancer therapy.

3. PATIENT SELECTION

3.1 Target Population

The target population is men with prostate cancer who have experienced a rising PSA (biochemical recurrence) after definitive local therapy with a radical prostatectomy. This population will not have evidence of metastatic disease on CT scan and NM bone scan. Furthermore, the population will be high risk for development of metastatic disease, as defined by a PSA doubling time (PSADT) of < 6 months and an absolute PSA value of ≥1.0 ng/ml.

3.2 Expected Enrollment

A total of 50 patients will be included in this study. The first patients are expected to be enrolled in March 2017. Accrual is expected to be completed in 24 months, or earlier, once the protocol has been approved by the IRB at each participating institution.

3.3 Inclusion Criteria

To be included in this study, patients should meet all of the following criteria:

- Willing and able to provide written informed consent and HIPAA authorization for the release of personal health information. Provision of informed consent prior to any study procedures.

NOTE: HIPAA authorization may be either included in the informed consent or obtained separately.

- Males aged 18 years of age and above
- Histological proof of adenocarcinoma of the prostate
- Prior local therapy with prostatectomy required, with available tissue from prostatectomy specimen to send for genomic and transcriptomic testing. Specifically, either FFPE blocks or 35-40 unstained slides from the primary prostatectomy specimen will need to be available for central pathologic review and processing.
- Prior salvage or adjuvant radiation therapy is allowed but not mandated. Radiation therapy must have been completed for at least 6 months.
- Absolute PSA ≥ 1 ng/ml. Prior undetectable PSA post-prostatectomy is not required.
- PSADT ≤ 6 months, based upon ≥ 3 consecutive measurements collected in the past 12 months, at least 4 weeks apart, calculating using the MSKCC calculator (<https://www.mskcc.org/nomograms/prostate/psa-doubling-time>)
- No radiographic evidence of metastatic disease by CT scan and bone scan, performed within the prior 4 weeks.
- Serum testosterone ≥ 150 ng/dl.
- Participants must have normal organ and bone marrow function measured within 28 days prior to administration of study treatment as defined below:
 - Hemoglobin ≥ 10.0 g/dL with no blood transfusion in the past 28 days
 - Absolute neutrophil count (ANC) $\geq 1.5 \times 10^9/L$
 - Platelet count $\geq 75 \times 10^9/L$
 - Total bilirubin $\leq 1.5 \times$ institutional upper limit of normal (ULN)
 - Aspartate aminotransferase (AST) (Serum Glutamic Oxaloacetic Transaminase (SGOT)) / Alanine aminotransferase (ALT) (Serum Glutamic Pyruvate Transaminase (SGPT)) $< 2.5 \times$ institutional upper limit of normal

Note: Patients with elevations in bilirubin, AST, or ALT should be thoroughly evaluated for the etiology of this abnormality prior to entry and patients with evidence of viral infection should be excluded.

- Participants must have creatinine clearance estimated using the Cockcroft-Gault equation of ≥ 51 mL/min:

$$\text{Estimated creatinine clearance} = \frac{(140 - \text{age [years]}) \times \text{weight (kg)}}{\text{serum creatinine (mg/dL)} \times 72}$$

Note: Patients with creatinine clearance between 51- 80 mL/min either at trial enrolment or during the course of the trial should be monitored every 2 weeks for laboratory assessment and toxicity evaluation.

- ECOG PS ≤ 1 . (Appendix A: Performance Status Criteria)
- Participants must have a life expectancy ≥ 16 weeks.

- Male participants and their partners, who are sexually active and of childbearing potential, must agree to the use of two highly effective forms of contraception in combination [see appendix E for acceptable methods], throughout the period of taking study treatment and for 3 months after last dose of study drug to prevent pregnancy in a partner.
- *For enrichment stage of trial only (if necessary):* Confirmation of a suspected/known deleterious mutation in a gene of interest (ATM, BARD1, BRCA1, BRCA2, BRIP1, CDK12, CHEK1, CHEK2, FANCL, PALB2, PPP2R2A, RAD51B, RAD51C, RAD51D or other DNA repair genes) via CLIA certified testing.

3.4 Exclusion Criteria

Patients that meet any of the criteria listed below will not be eligible for study entry:

- Metastatic disease or currently active second malignancy
- Prior ADT in the past 6 months. Prior ADT in context of neoadjuvant/adjuvant primary; prior ADT for biochemical recurrence is allowed, as long as no ADT has been administered in past 6 months and testosterone has recovered (>150 ng/dl). The total duration of prior ADT should not exceed 24 months.
- Prior oral anti-androgen (e.g. bicalutamide, nilutamide, enzalutamide, apalutamide), or androgen synthesis inhibitor (e.g. abiraterone, orteronel) in the past 6 months. 5-alpha reductase inhibitor therapy (e.g. finasteride, dutasteride) is allowed, as long as subject has been stable on medication for past 6 months.
- Prior treatment with intravenous chemotherapy.
- Use of any prohibited concomitant medications (Appendix B: Medications With the Potential for Drug-Drug Interactions) within the prior 2 weeks.
- Involvement in the planning and/or conduct of the study (applies to both AstraZeneca staff and/or staff at the study site)
- Previous enrolment in the present study
- Participation in another clinical study with an investigational product during the last 1 month.
- Any previous treatment with PARP inhibitor, including olaparib.
- Resting ECG with QTc > 470 msec on 2 or more time points within a 24 hour period or family history of long QT syndrome
- Concomitant use of known strong CYP3A inhibitors (eg. itraconazole, telithromycin, clarithromycin, protease inhibitors boosted with ritonavir or cobicistat, indinavir, saquinavir, nelfinavir, boceprevir, telaprevir) or moderate CYP3A inhibitors (eg. ciprofloxacin, erythromycin, diltiazem, fluconazole, verapamil). The required washout period prior to starting olaparib is 2 weeks. During the study, if co-administration of a strong or moderate inhibitor is required because there is no suitable alternative medication, exception to this criterion may be allowed with a suitable dose reduction of olaparib (see section 5.5.2.1)
- Concomitant use of known strong CYP3A inducers (eg. phenobarbital, phenytoin, rifampicin, rifabutin, rifapentine, carbamazepine, nevirapine and St John's Wort) or

moderate CYP3A inducers (eg. bosentan, efavirenz, modafinil). The required washout period prior to starting olaparib is 5 weeks for phenobarbital and 3 weeks for other agents.

- Persistent toxicities (>Common Terminology Criteria for Adverse Event (CTCAE) grade 2) caused by previous cancer therapy, excluding alopecia.
- Patients with myelodysplastic syndrome/acute myeloid leukaemia or with features suggestive of MDS/AML.
- Major surgery within 2 weeks of starting study treatment and patients must have recovered from any effects of any major surgery.
- Poor medical risk due to a serious, uncontrolled medical disorder, non-malignant systemic disease or active, uncontrolled infection. Examples include, but are not limited to, uncontrolled ventricular arrhythmia, recent (within 3 months) myocardial infarction, uncontrolled major seizure disorder, extensive interstitial bilateral lung disease on High Resolution Computed Tomography (HRCT) scan or any psychiatric disorder that prohibits obtaining informed consent.
- Unable to swallow orally administered medication and patients with gastrointestinal disorders likely to interfere with absorption of the study medication.
- Immunocompromised patients, e.g., patients who are known to be serologically positive for human immunodeficiency virus (HIV).
- Known hypersensitivity to olaparib or any of the excipients of the product.
- Known active hepatitis (i.e. Hepatitis B or C) due to risk of transmitting the infection through blood or other body fluids
- Whole blood transfusions in the last 120 days prior to entry to the study (packed red blood cells and platelet transfusions are acceptable, for timing refer to inclusion criteria no.10)

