 - Total bilirubin $\leq 1.5 \times$ institutional upper limit of normal (ULN)
 - Aspartate aminotransferase (AST) (Serum Glutamic Oxaloacetic Transaminase (SGOT)) / Alanine aminotransferase (ALT) (Serum Glutamic Pyruvate Transaminase (SGPT)) $< 2.5 \times$ institutional upper limit of normal

Note: Patients with elevations in bilirubin, AST, or ALT should be thoroughly evaluated for the etiology of this abnormality prior to entry and patients with evidence of viral infection should be excluded.

- Patients must have creatinine clearance estimated using the Cockcroft-Gault equation of ≥ 51 mL/min:
Estimated creatinine clearance = $\frac{(140 - \text{age [years]}) \times \text{weight (kg)}}{\text{serum creatinine (mg/dL)} \times 72}$

9. Eastern Cooperative Oncology Group (ECOG) performance status 0-1 (see Appendix A).
10. Male participants and their partners, who are sexually active and of childbearing potential, must agree to the use of two highly effective forms of contraception in combination [see appendix E for acceptable methods], throughout the period of taking study treatment and for 3 months after last dose of study drug to prevent pregnancy in a partner.
11. *For enrichment stage of trial only (if necessary):* Confirmation of a suspected/known deleterious mutation in a gene of interest (ATM, BARD1, BRCA1, BRCA2, BRIP1, CDK12, CHEK1, CHEK2, FANCL, PALB2, PPP2R2A, RAD51B, RAD51C, RAD51D, or other DNA repair genes) via CLIA certified testing.

Exclusion:

1. Prior ADT in the past 6 months. Prior ADT in context of neoadjuvant/adjuvant primary; prior ADT for biochemical recurrence is allowed, as long as no ADT has been administered in past 6 months and testosterone has recovered (>150 ng/dl). The total duration of prior ADT should not exceed 24 months.

2. Prior oral anti-androgen (e.g. bicalutamide, nilutamide, enzalutamide, apalutamide), or androgen synthesis inhibitor (e.g. abiraterone, orteronel) in the past 6 months. 5-alpha reductase inhibitor therapy (e.g. finasteride, dutasteride) is allowed, as long as subject has been stable on medication for past 6 months.
3. Prior treatment with intravenous chemotherapy for prostate cancer.
4. Involvement in the planning and/or conduct of the study (applies to both AstraZeneca staff and/or staff at the study site)
5. Participation in another clinical study with an investigational product during the last 1 month.
6. Any previous treatment with PARP inhibitor, including olaparib.

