- vi. Time to next anti-cancer therapy analysis: similarly to MFS, this time to event analysis will be estimated using the Kaplan-Meier method.

(f) Sample size justification: The study will enroll up to 50 subjects. The design is a multi-stage adaptive design, with stage sizes and decision rules calculated based upon assumptions for hypothesis testing for the primary endpoint.

The sample sizes for each stage are chosen to allow for interim assessment of the primary endpoint, in order to adapt if the unselected population results are suggestive of futility. In the case of futility in the all-comer population, a biomarker-selected stage can proceed. The operating characteristics of the design were assessed in a 10,000-iteration simulation, assuming biomarker prevalence is 10-15%. This design will have 0.90-0.91 power for the unselected population and a 0.79-0.80 power for the biomarker-selected population when no effect in the selected population. The overall type 1 error is 0.1 – 0.11,. The type 1 error for the biomarker-selected population is 0.04.

The trial will also employ an early stopping rule for an AE of special interest. If >1 patient is diagnosed with myelodysplastic syndrome or acute myeloid leukemia during the trial, then the trial is to be stopped.

Funding, Regulatory, and Feasibility Issues: AstraZeneca is providing funding for performance of the clinical trial as well as providing olaparib to patients. IND will be filed and held by the principle investigator, [name].

Patient Acceptability/Ethics and Consent Issues: This trial will be an alternative option for intervention other than standard therapies of ADT or surveillance. Olaparib has rare but life threatening side effects including MDS/AML in <1% of patients treated; by monthly laboratory monitoring and exclusion of patients with prior chemotherapy, we aim to minimize this risk. Additionally, by performing this trial in the highest risk patients with biochemically recurrent prostate cancer and by exclusion prior DNA-damaging chemotherapy, the potential benefits of a new therapy option with olaparib is more likely to outweigh risks, than if this trial were performed in patients with less risk for morbidity and mortality from prostate cancer.

TABLE OF CONTENTS

[Press F9 to update]

1.1	Disease Background	16
1.2	Treatment Background	17
1.3	Rationale for olaparib in high risk biochemically recurrent prostate cancer	20
2. OBJECTIVES		22
2.1	Primary Objective	22

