Note: Patients with elevations in bilirubin, AST, or ALT should be thoroughly evaluated for the etiology of this abnormality prior to entry and patients with evidence of viral infection should be excluded.

- Participants must have creatinine clearance estimated using the Cockcroft-Gault equation of ≥ 51 mL/min:

$$\text{Estimated creatinine clearance} = \frac{(140 - \text{age [years]}) \times \text{weight (kg)}}{\text{serum creatinine (mg/dL)} \times 72}$$

Note: Patients with creatinine clearance between 51- 80 mL/min either at trial enrolment or during the course of the trial should be monitored every 2 weeks for laboratory assessment and toxicity evaluation.

- ECOG PS \leq 1. (Appendix A: Performance Status Criteria)
- Participants must have a life expectancy \geq 16 weeks.
- Male participants and their partners, who are sexually active and of childbearing potential, must agree to the use of two highly effective forms of contraception in combination [see appendix E for acceptable methods], throughout the period of taking study treatment and for 3 months after last dose of study drug to prevent pregnancy in a partner.
- *For enrichment stage of trial only (if necessary):* Confirmation of a suspected/known deleterious mutation in a gene of interest (ATM, BARD1, BRCA1, BRCA2, BRIP1, CDK12, CHEK1, CHEK2, FANCL, PALB2, PPP2R2A, RAD51B, RAD51C, RAD51D or other DNA repair genes) via CLIA certified testing.

3.4 Exclusion Criteria). The following assessments will be performed at this visit:

- obtain informed consent and research authorization
- record demographics (including age) and medical history (including prior treatment for prostate carcinoma)
- conduct physical exam (including vital signs, height/weight)
- obtain history regarding prior treatment history for prostate cancer (including history of ADT, history of radiation therapy or other local therapy, and prior PSA history to calculate PSADT).
- obtain histologic confirmation of disease, and radiographic evidence of lack of metastatic disease. If radiographic studies have not been performed in prior 4 weeks, they must be obtained as part of screening.
- perform laboratory tests: Complete blood count w/Diff, PSA, Comprehensive metabolic panel, urinalysis, PT/INR, PTT, testosterone.
- PSA doubling time will be confirmed using MSKCC calculator (<https://www.mskcc.org/nomograms/prostate/psa-doubling-time>)
- assess performance status (ECOG). (Appendix A)

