5.9 Concomitant Medications

The use of any natural/herbal products or other traditional remedies should be discouraged, but use of these products, as well as use of all vitamins, nutritional supplements, and all other concomitant medications must be recorded in the case report form (CRF).

Medications that may NOT be administered:

- No other anti-cancer therapy (chemotherapy, immunotherapy, hormonal therapy (Hormone replacement therapy (HRT) is acceptable), radiotherapy, biological therapy or other novel agent) is to be permitted while the patient is receiving study medication.
- Live virus and live bacterial vaccines should not be administered whilst the patient is receiving study medication and during the 30 day follow up period. An increased risk of infection by the administration of live virus and bacterial vaccines has been observed with conventional chemotherapy drugs and the effects with olaparib are unknown.

Restricted concomitant medications

Strong or Moderate CYP3A inhibitors

Known strong CYP3A inhibitors (e.g., itraconazole, telithromycin, clarithromycin, boosted protease inhibitors, indinavir, saquinavir, nelfinavir, boceprevir, telaprevir) or moderate CYP3A inhibitors (ciprofloxacin, erythromycin, diltiazem, fluconazole, verapamil) should not be taken with olaparib. During the study, if co-administration of a strong or moderate inhibitor is required because there is no suitable alternative medication, exception to this criterion may be allowed with a suitable dose reduction of olaparib (see section 5.5.2.1)

Strong or Moderate CYP3A inducers

Strong (e.g., phenobarbital, phenytoin, rifampicin, rifabutin, rifapentine, carbamazepine, nevirapine, enzalutamide and St John's Wort) and moderate CYP3A inducers (eg. bosentan, efavirenz, modafinil) of CYP3A should not be taken with olaparib.

P-gp inhibitors

It is possible that co-administration of P-gp inhibitors (eg amiodarone, azithromycin) may increase exposure to olaparib. Caution should therefore be observed.

Effect of olaparib on other drugs

Based on limited in vitro data, olaparib may increase the exposure to substrates of CYP3A4, P-gp, OATP1B1, OCT1, OCT2, OAT3, MATE1 and MATE2K.

Based on limited in vitro data, olaparib may reduce the exposure to substrates of CYP3A4, CYP1A2, 2B6, 2C9, 2C19 and P-gp.

Caution should therefore be observed if substrates of these isoenzymes or transporter proteins are co-administered.

Examples of substrates include:

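### Section 3.4 bars prior chemotherapy only if it was intravenous, so the criteria fall slightly short of the MDS/AML safeguard that the synopsis describes

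*Combined protocol and SAP*

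**What the plan says.** Section 3.4, the list that screening (Section 5.1) points to, excludes "Prior treatment with intravenous chemotherapy". It limits the route but not the indication or the time since treatment. Synopsis exclusion 3 reads "Prior treatment with intravenous chemotherapy for prostate cancer", which limits both route and indication.

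The rationale is in the synopsis under Patient Acceptability/Ethics and Consent Issues. It calls MDS/AML rare but life threatening and names two mitigations: monthly laboratory tests and "exclusion of patients with prior chemotherapy, we aim to minimize this risk". It then gives two grounds for the balance of benefit and risk. One is that the trial enrols the men at highest risk among those with biochemical recurrence. The other is worded "by exclusion prior DNA-damaging chemotherapy, the potential benefits of a new therapy option with olaparib is more likely to outweigh risks". Neither statement about chemotherapy mentions a route or an indication.

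At screening, Section 5.1 asks the site to "obtain history regarding prior treatment history for prostate cancer (including history of ADT, history of radiation therapy or other local therapy", together with the PSA history. It also calls for a general medical history and a judgement on whether olaparib is suitable for the patient.

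**The concern.** The protocol tells its readers, including ethics committees, that prior chemotherapy is excluded in order to limit a life-threatening risk. The rule that sites apply excludes less than that. A site that follows Section 3.4 exactly could enrol a man whom the rationale describes as excluded.

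The exclusion is also the only stated MDS/AML safeguard that restricts earlier exposure. The others act on existing disease or damage, or after treatment starts: the exclusions for MDS/AML and persistent toxicity, the marrow thresholds, the blood counts, the work-up of prolonged cytopenia, and the rule that stops the trial after more than 1 case. They do not replace a restriction on prior exposure.

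**Working it through.** No power, sample-size or error-rate figure is involved, so the main check is a comparison of texts. A short calculation of the accrual cost follows.

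**1. Is the word 'intravenous' meant literally?** The surrounding text suggests that a site would read it so. The neighbouring criterion in Section 3.4 also names a route where it wants one: "Prior oral anti-androgen (e.g. bicalutamide, nilutamide, enzalutamide, apalutamide), or androgen synthesis inhibitor". Where no route limit is intended, none is written: "Any previous treatment with PARP inhibitor, including olaparib". The ban on concurrent treatment in Section 5.9 has no route limit for chemotherapy either: "No other anti-cancer therapy (chemotherapy, immunotherapy, hormonal therapy".

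**2. How do the texts treat different histories?**

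| Prior treatment | Section 3.4 | Synopsis exclusion list | Synopsis rationale |
|---|---|---|---|
| Intravenous chemotherapy for prostate cancer | Excluded | Excluded | Excluded |
| Intravenous chemotherapy for another cancer, no longer active | Excluded | Not excluded | Excluded |
| Oral DNA-damaging chemotherapy for another cancer, no longer active | Not excluded | Not excluded | Excluded |
| Oral DNA-damaging chemotherapy for a non-cancer condition | Not excluded | Not excluded | Excluded as worded |
| Oral chemotherapy for another cancer that is still active | Excluded, through the second-malignancy criterion | Not excluded | Excluded |

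Rows 3 and 4 are the gap. Rows 2 and 5 are differences between the two lists. They have no practical effect where a site applies both, because Section 3.4 is then the stricter one.

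**3. Does another criterion close rows 3 and 4?** Sections 3.3 and 3.4 contain no other item on past chemotherapy. The Section 5.1 treatment-history item concerns prostate cancer and does not name chemotherapy. The general medical history may bring an oral exposure to light, but under the present wording that exposure would not exclude the man.

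**4. Can the effect on MDS/AML be computed?** No. Section 1.2.4 gives 22 cases in 2618 olaparib patients (22/2618 = 0.84%) and 6 cases in a study of 298 patients (6/298 = 2.0%). Neither rate is split by prior chemotherapy, and the documents do not say how many men in this population have had oral DNA-damaging treatment.

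**5. What would closing the gap cost in accrual?** Assume that 0%, 1% or 2% of otherwise eligible men have such exposure; the documents give no figure.

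- Men lost per 50: 50 × 0 = 0; 50 × 0.01 = 0.5; 50 × 0.02 = 1.0.
- Time to replace 1 man at the 1 to 2 patients per month in the synopsis: 1/2 = 0.5 month to 1/1 = 1 month.
- Share of the 24-month accrual plan: 0.5/24 = 2.1% to 1/24 = 4.2%.
- At the pace implied by the full plan, 50/24 = 2.08 per month, so 1 man takes 1/2.08 = 0.48 month.

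**The case against.** The case on the other side is that this is a matter of wording with almost no consequence. The ethics paragraph is rationale, not an operative rule, and can be read as shorthand for the exclusion listed in the same synopsis. A man with another active cancer, a plausible source of oral chemotherapy, is already excluded by Section 3.4. The investigator must judge suitability for olaparib, and further criteria exclude men who are poor medical risks or immunocompromised. An illustration shows the scale: if the 2% rate from the 298-patient study applied to 1 affected man, the expected number of cases would be 0.02, about 0.012 more than at the overall rate (0.020 − 0.008). At five times that rate it would be 0.1.

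Much of this stands. The affected group is small, and the differences between the two lists have no practical effect. What does not stand is the shorthand reading as a full answer. The rationale names DNA-damaging chemotherapy as the exposure of concern, and the route by which a drug was given does not change whether it damages DNA. A suitability judgement is not an exclusion. The illustration borrows a rate that is not specific to prior exposure, so it shows scale and is not an estimate.

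A reader might infer more than the documents allow:

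- *That the gap leads to excess MDS/AML.* The documents give no rate by prior chemotherapy, and Section 7.5 states that the programme's data do not support a causal link with olaparib.
- *That the whole balance of benefit and risk rests on this exclusion.* It is one of two grounds; the other, enrolment of the highest-risk men, is argued again in Section 1.3.2 and is untouched.
- *That men treated intravenously for another cancer can enter.* Section 3.4 excludes them.

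**Conclusion.** The point holds as a minor safety-consistency gap. Both exclusion lists admit a man with past oral DNA-damaging chemotherapy, for a cancer no longer active or for a non-cancer indication, whereas the synopsis rationale describes such exposure as excluded. This rests on reading 'intravenous' literally, which the neighbouring criteria support. Few men are likely to be affected. The size of any effect on MDS/AML cannot be computed from the documents and none is claimed, and the PSA50 decision rules and operating characteristics are unchanged. The gap merits correction because the protocol chose this safeguard itself, against a risk that it calls life threatening, and because correction is nearly free.

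**What to change.** In both Section 3.4 and synopsis exclusion 3, use one wording: *Prior systemic (oral or parenteral) cytotoxic or DNA-damaging chemotherapy for any indication.* 'Systemic' avoids excluding men who had only local or topical agents, which 'any route' would do. The shared wording also removes the prostate-cancer limit from the synopsis.

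In the Section 5.1 history item, add: *any prior systemic chemotherapy, for any indication.* What is asked at screening then matches what is excluded, including non-cancer use.

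If the sponsor intends the intravenous limit, the alternative is to state and justify it in the ethics paragraph.

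The cost is one line in each of three places and a very small loss of eligible men: about 0 to 1 per 50 on the assumed 0% to 2% exposure, or at most about one month of accrual.
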